## 5.2 Primary Safety Endpoint

The study's primary safety endpoint is the proportion of subjects with adverse events rated as probably or definitely related to the study procedure classified as Clavien-Dindo Grade 2 or higher or any Grade 1 event resulting in persistent disability (e.g. incontinence, ejaculatory disorder, or erectile dysfunction) evidenced through 3 months post treatment. Note that the Clavien-Dindo classification scheme is for grading postoperative complications, not events that reflect lack of treatment efficacy. The endpoint is adjudicated by the study's clinical events committee (CEC).

The study's primary endpoint hypothesis is a one-way statistical test (alpha=.025 for interpretation):

$$\begin{aligned}
 H_0: \text{Mean (safety rate at 3 months)} &\geq 65\% \\
 H_a: \text{Mean (safety rate at 3 months)} &< 65\%
 \end{aligned}$$

An exact binomial test (binom.test in R) will be used to determine the P-value for the above comparison. Power calculations showed that the primary safety endpoint with 90 evaluable subjects has an 80% power to detect a safety rate of less than 65%.

The primary safety endpoint is calculated using the mITT population.

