### ***4.2 Primary Endpoint Calculation and Sample Size Determination***

Prior studies have shown that IPSS scores are reduced by approximately 16 points after Aquablation, values similar to those observed after TURP. In patients with moderate-to-severe BPH, the mean change in IPSS score representing slight improvement is approximately 5 points. Therefore, showing a mean reduction in IPSS scores that statistically exceeds  $16-5 = 11$  points will be interpreted as study success. The study's primary endpoint hypothesis is a one-way statistical test (alpha=.025 for interpretation):

$$\begin{aligned} H_0: \text{Mean(IPSS change score at 3 months)} &\leq 11 \\ H_a: \text{Mean(IPSS change score at 3 months)} &> 11 \end{aligned}$$

With 100 patients and assuming 10% subjects lost to follow, 90 evaluable subjects with an underlying change of 16 points and a change score SD of 7.5 points yields a 99% power to detect an improvement of more than 11 points.

The WATER study (IDE#G150089) used an assumption that a TURP rate for the same safety definition provided in this protocol would be 65% for a range of prostate sizes 30-80mL. The same safety target will be used for this protocol treating large prostates of 80-150mL. The assumed true rate for the Aquablation patients will be 50% (10% greater than WATER in order to account for treating larger prostates). The study's primary endpoint hypothesis is a one-way statistical test (alpha=.025 for interpretation):

$$\begin{aligned} H_0: \text{Mean (safety rate at 3 months)} &\geq 65\% \\ H_a: \text{Mean (safety rate at 3 months)} &< 65\% \end{aligned}$$

The primary safety endpoint with 90 evaluable subjects has an 80% power to detect a safety rate of less than 65%.

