#### **4.1 Modified Intent-to-Treat (mITT) Cohort**

The mITT population includes all enrolled subjects in whom the Aquablation handpiece is inserted into the penile urethra. A patient found at the time of the procedure to have a condition that results in study exclusion does not contribute to the mITT cohort. The mITT population is the primary analysis population for both the primary safety and effectiveness endpoints.

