#### **4.2 Per-protocol (PP) Cohort**

The per-protocol (PP) population is all mITT subjects who:

1. meet critical study eligibility criteria;
2. have no significant protocol deviations that could affect the validity of data; and
3. have evaluable assessment for the endpoint of interest.

A significant protocol deviation means non-adherence on the part of the subject or investigator to clinically significant protocol-specific inclusion/exclusion criteria, primary objective variable criteria or critical study requirements that could affect the scientific validity of the observed data point or lead to bias. Missing data are not imputed for analyses with the PP cohort.

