## **5 STUDY ENDPOINTS**

### **5.1 Primary Effectiveness Endpoint**

The primary effectiveness endpoint is the IPSS change score from baseline to 3 months. IPSS is an accepted and commonly used measure for symptom severity in BPH. IPSS varies from 0 (no symptoms) to 35 (maximal symptoms). The mean 3-month IPSS change score (abbreviated dIPSS3) in WATER was 16 points (SD=7 points). WATER used a non-inferiority margin of 5 points; 5 points represents the minimum change for men with moderate-to-severe BPH that is detectable. The current study's goal is therefore to show that the IPSS change score statistically exceeds 16-5 = 11 points. The study's hypotheses are therefore:

$$\begin{aligned} H_0: \text{dIPSS}_3 &\leq 11 \\ H_a: \text{dIPSS}_3 &> 11 \end{aligned}$$

A one-way t test with the mITT cohort will be used for the calculation. With 100 patients and assuming 10% subjects lost to follow, 90 evaluable subjects with an underlying change of 16 points and a change score SD of 7.5 points yields a 99% power to detect an improvement of more than 11 points.

A secondary goal is to show similarity of change scores between WATER II and WATER. Data from WATER and WATER II will be combined. Regression analyses controlling for baseline IPSS score (a strong predictor of change scores) will calculate differences in change scores between WATER and WATER II subjects. WATER II will be determined to have similar dIPSS3 scores if the 95% confidence limits for the difference between WATER and WATER II Aquablation subjects exceeds -5 points. The study is not necessarily powered for this comparison.

Missing data for dIPSS3 will be imputed using the following rules:

- Predicted value from baseline IPSS: In WATER, dIPSS3 was strongly and statistically significantly related to baseline IPSS (Figure 1). This finding is not surprising for maximally effective procedures that reduce scores to close to maximal (i.e., a ceiling effect). A linear regression model using WATER II available data will be used to predict missing change scores.
- Low value: A change score of 0 points
- High value: a change of 5 less than the maximal possible improvement, which represents change scores from WATER (see also Figure 1)

[figure not shown]

Figure 1. Relationship between baseline IPSS and 3-month change score in WATER. Blue = Aquablation, red = TURP.

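### Does the primary safety test need a written rule for men whose safety status at 3 months is unknown?

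*SAP*

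**What the plan says.** SAP 5.2 defines the endpoint as the proportion of men with qualifying procedure-related events "evidenced through 3 months post treatment", adjudicated by the clinical events committee. The test is exact binomial, one-sided at 0.025, against 65%, and "The primary safety endpoint is calculated using the mITT population". Of that cohort, SAP 4.1 says: "The mITT population includes all enrolled subjects in whom the Aquablation handpiece is inserted into the penile urethra". It sets no requirement for 3-month data.

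The power sentence in SAP 5.2 says that "the primary safety endpoint with 90 evaluable subjects has an 80% power". Protocol 4.2 shows where the 90 comes from: "With 100 patients and assuming 10% subjects lost to follow, 90 evaluable subjects". Protocol 4.2 also gives the assumed true rate, 50%.

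The rules on missing data lie elsewhere. In SAP 5.1, missing 3-month IPSS changes "will be imputed using the following rules". In SAP 4.2, only per-protocol men must "have evaluable assessment for the endpoint of interest", and "Missing data are not imputed for analyses with the PP cohort". Protocol 4.1 refers back to denominators listed earlier, but none is listed for this endpoint.

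Protocol 2.20 and Table 2 collect adverse events at treatment, at discharge and at every visit, covering all events through 12 months. Protocol 2.22 treats a man as lost only if he cannot be reached and has missed two visits in a row. Protocol 2.11 gives 101 treated men.

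**The concern.** This is one of two primary hypotheses, and success means showing a low event rate. Two readings are open. Reading A takes the mITT denominator literally, so a man with no recorded event and unknown status counts as event-free. Reading B leaves such men out, as the power basis suggests. Compared with complete follow-up, A can only lower the observed rate. The endpoint also includes Grade 1 events that cause persistent disability, and persistence cannot be established in a man who disappears early. The authors wrote three imputation rules for effectiveness and none for safety. If the choice were made after the data were seen, a borderline result could turn on it.

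**Working it through.** **Inputs.** Null rate 65%, one-sided alpha 0.025 (SAP 5.2). Assumed true rate 50%, 10% loss, 90 evaluable of 100 (Protocol 4.2). 101 treated (Protocol 2.11). Two inputs are assumptions: L, the number of men lost, and s, the share of their qualifying events already recorded.

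**The plan's own figure.** For n = 90:
- Wald approximation: Φ(0.15/√(0.25/90) − 1.96) = Φ(0.886) = 81.2%.
- Continuity-corrected: Φ((0.15 − 0.5/90 − 1.96·√(0.65·0.35/90))/√(0.25/90)) = 80.8%.
- Exact test, passing at 49 or fewer events: size 2.48%, power 82.9%.

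The stated 80% is reproduced. The 90 is simply 100 × 0.9, and effectiveness pairs the same 90 with mITT.

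**Pass limits.** The limit c is the largest count with P(Bin(n, 0.65) ≤ c) ≤ 0.025.

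| n | c | Size | Power at 50% |
|---|---|---|---|
| 90 | 49 | 2.48% | 82.9% |
| 91 | 49 | 1.83% | 79.9% |
| 100 | 55 | 2.46% | 86.4% |
| 101 | 55 | 1.84% | 84.0% |

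**Reading A (unknowns event-free).** Observed events are X = Bin(N − L, 0.65) + Bin(L, 0.65·s), and the trial passes if X ≤ 55. Type I error:

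| N | L | s = 50% | s = 75% | s = 90% |
|---|---|---|---|---|
| 101 | 10 | 7.6% | 4.0% | 2.5% |
| 101 | 5 | 3.9% | 2.7% | 2.2% |
| 100 | 10 | 9.5% | 5.2% | 3.4% |
| 100 | 5 | 5.1% | 3.6% | 2.9% |

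With one man lost at N = 101 and none of his events recorded, it is 2.46%. If every event in lost men is recorded (s = 100%), reading A is exactly the full-follow-up test: 1.84% size and 84.0% power. The N = 100 rows look worse partly because the discrete test starts there at 2.46% rather than 1.84%.

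**Reading B (unknowns excluded).** With 10 of 101 lost and loss unrelated to events, n = 91 and the error is 1.83%. If the overall rate is 65% but lost men have rate q, the assessed rate is (0.65·101 − 10q)/91:
- q = 75%: 58.15/91 = 63.9%, error 3.1%.
- q = 80%: 57.65/91 = 63.4%, error 4.0%.

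**The alternative rule.** Suppose the denominator were men of known status plus lost men with a recorded event. With N = 101 and L = 10, the expected rate when the truth is 65% is (91·0.65 + 6.5s)/(91 + 6.5s). That is 62.4/94.25 = 66.2% at s = 50% and 65.65/97.5 = 67.3% at s = 100%, so it is biased upward. Type I error falls to 1.05% (s = 50%) and 0.5% (s = 100%). Power at a 50% rate falls to 74.5% and 67.7%. The loss is greatest when recording is complete, which is when mITT as written is exactly right.

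**The case for a change.** The strongest case is that the mITT label says who belongs in the analysis but not how an unknown outcome is scored, and that the plan itself expects 10% loss. With 101 men and 11 unknown, the pass limit is 49 observed events of 90 if the unknowns are dropped and 55 if they count as event-free. A count from 50 to 55 therefore passes under one reading and fails under the other. Dropping all lost men also discards events already recorded, and it inflates the error if lost men do worse.

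The missing rule stands. The size of the problem does not follow from it. The 50-to-55 band assumes 11 men unknown with none of their events recorded, and the planned result (50%, or 45 of 90) passes under both readings. Follow-up as written works against that assumption. Events are sought at treatment, discharge and 1 month, and a man who misses only the 3-month visit is still followed, so his later record can settle his status. Withdrawal under Protocol 2.21 can still leave some men unknown, but nothing in the documents suggests that half of their events would go unseen.

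Nor does reading A always favour a pass relative to reading B, because A keeps recorded events in lost men that B throws away.

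**Conclusion.** No change to the plan follows. SAP 5.2 leaves a detail unstated, and an analyst would ordinarily fill it by using the whole adverse-event record to settle status and then working in mITT or among men of known status.

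At N = 101, reading B keeps the error at 1.83% with 10 lost if loss is unrelated to events, and at 3.1% or 4.0% if lost men's rate is 75% or 80%. Reading A gives 2.5% or less with 5 to 10 lost when 90% of their events are recorded. It reaches 4.0% to 7.6% only with 10 lost and a quarter to a half of their events unrecorded. At the planning figure of 100 men, reading A stays somewhat above nominal even at 90% recorded (2.9% with 5 lost, 3.4% with 10).

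The alternative denominator is a debatable trade: it depends on the outcome, and it brings power below the stated 80%. Reporting the number of unknowns, or adding a tipping-point analysis, would be reasonable but would leave the pass/fail result unchanged. The conclusion rests on few men being of unknown status and on most of their events being recorded. If the actual number of unknowns proved near 10 and their follow-up ended very early, a borderline safety result would need to be read with that in mind.

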## 6 SECONDARY ENDPOINT ASSESSMENTS

The following secondary endpoints are calculated.

### 6.1 Procedure Time

Length of procedure time as defined as AQUABEAM handpiece insertion to insertion of indwelling catheter. Mean and 95% confidence intervals will be calculated. There is no statistical hypothesis for this endpoint; it is considered informational.

## **6.2 Ejaculatory or Erectile Dysfunction**

Proportion of subjects who were sexually active at baseline and experienced either ejaculatory or erectile dysfunction (per protocol definitions) at 3 months as adjudicated by the CEC as possibly, probably or definitely related to the study procedure. An exact binomial confidence interval will be calculated using binom.test or CIbinomial; there is no statistical hypothesis. Because ejaculatory and erectile dysfunction after prostate surgery are likely to have different underlying causes, similar calculations will be performed for each event type. Because there can be other causes (apart from surgery), further calculations will exclude subjects in whom the CEC determines that the event is unrelated (i.e., judged as neither possibly, probably or definitely related).

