## **2.20 Adverse events**

The occurrence of all adverse events will be documented in all study subjects throughout the study treatment and 12 months follow-up period. Only urological SAEs and urological events will be collected at 24 months, 36 months, 48 months, and 60 months follow-up visits. AE information (start and stop date, description of event, severity, relatedness to the treatment procedure, the device itself or other study-related procedures) will be assessed and recorded on CRFs. Whether an AE meets the definition for serious adverse event will be determined by the study investigator using **Table 3**. All urological events consistent with a SAE must be reported to the Sponsor within 24 hours of awareness of the event. Relatedness of the AE to the surgical procedure or the study device itself will be judged by the clinical events committee (CEC) for adverse events up to 12 months according to **Table 4**.

The classification of surgical complications shall be done per **Table 5** by the CEC. Note that persistent ejaculatory or erectile dysfunction, the need for re-catheterization after postoperative day 3, and urinary incontinence related to surgery are considered to be surgical complications.

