**Table 4 Adverse event relatedness categories**

| Term       | Definition   |
|------------|--|
| Unrelated  | No evidence that AE related to Aquablation procedure or AQUABEAM System  |
| Unlikely   | AE has a low likelihood of being related to Aquablation procedure or AQUABEAM System                               |
| Possible   | AE could be related to Aquablation procedure or AQUABEAM System but an alternative explanation is also likely      |
| Probably   | AE likely to be related Aquablation procedure or AQUABEAM System even though alternative explanations are possible |
| Definitely | AE almost certainly related to Aquablation procedure or AQUABEAM System  |

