### ***3.2 Primary Safety Endpoint***

The primary safety endpoint is the proportion of subjects with adverse events rated as probably or definitely related to the study procedure classified as Clavien-Dindo Grade 2 or higher or any Grade 1 event resulting in persistent disability (e.g. ejaculatory disorder or erectile dysfunction) evidenced through 3 months post treatment. Note that the Clavien-Dindo classification scheme is for grading postoperative complications not events that reflect lack of effective treatment.

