### ***3.3 Secondary Endpoints for Marketing Claims***

Secondary endpoints are:

- Length of procedure time as defined as AQUABEAM Handpiece insertion to insertion of indwelling catheter. Mean and 95% confidence intervals will be calculated. There is no statistical hypothesis for this endpoint; it is considered informational.
- Proportion of subjects, who were sexually active at baseline and experienced either ejaculatory or erectile dysfunction (per protocol definitions) at 3 months. An exact binomial confidence interval will be calculated; there is no statistical hypothesis.
- Change from baseline to 3 months in Qmax. For a patient with a urinary catheter in place at the time testing, the Qmax value will be zero. Mean and confidence intervals will be calculated and a historical semi-quantitative comparison will be made with WATER Study data or other studies.

- Change from baseline to 3 months in PVR. For a patient with a urinary catheter in place at the time testing, the PVR value will be Not Applicable. Mean and confidence intervals will be calculated and a similar semi-quantitative comparison will be made.
- Change from baseline to 6 months in PSA. Mean and confidence intervals will be calculated. A t test will be used to compare PSA change vs. a null hypothesis of no change.
- Mean change from baseline in MSHQ-EjD score at 3 months. Preservation of ejaculatory function, meaning a change non-inferior to -4 points. A t test with 95% confidence intervals will be used to evaluate this hypothesis.
- Mean change from baseline in IIEF-5 (aka SHIM, part of IIEF-15) at 3 months. Preservation of erectile function, meaning a change score non-inferior to -6 points. An approach similar to that listed for MSHQ-EjD will be used.
- Re-intervention rate at 3 months. Re-intervention is defined as the need for additional tissue resection following the index procedure. An exact binomial confidence interval will be calculated. No statistical hypothesis is proposed.
- Subjects who entered the trial using a urinary catheter at any time 45 days prior to enrollment will yield more than 50% not needing a catheter at any time 45 days prior to the 3 months visit. An exact binomial confidence interval will be calculated. No statistical hypothesis is proposed.

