## **6 STUDY ADMINISTRATION**

### **6.1 Clinical Events Committee**

An independent Clinical Events Committee (CEC), consisting of three physicians who are not study Investigators will be utilized for this trial. This CEC will be responsible for the review and adjudication of reported adverse events up to 12 months related to the device or the procedure that occur over the course of the study per the CEC Charter. Additionally, the CEC may adjudicate other events at the request of the Data Monitoring Committee or Sponsor. The CEC adjudicators shall classify (assign relatedness) the above described adverse events based on severity and association to the procedure or other attribution.

Device- or procedure-related events which are associated with the secondary safety endpoint analysis will be as adjudicated by the CEC. In the event the CEC differs from the Investigator in classification of events, the resulting CEC adjudication will be used for final analysis and reporting.

A CEC Charter will be developed prior to the start of study enrollment. The CEC Charter shall include consistent definitions for each type of event and shall outline the review process.

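### SAP 6.2 limits the ejaculatory/erectile dysfunction proportion to procedure-related events, which conflicts with Protocol 3.3 and with the SAP section's own last sentence

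*SAP*

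**What the plan says.** Protocol 3.3 lists, among the secondary endpoints for marketing claims, the share of men sexually active at baseline who "experienced either ejaculatory or erectile dysfunction (per protocol definitions) at 3 months. An exact binomial confidence interval will be calculated". It states no hypothesis. The definitions it points to follow Protocol Table 3. Each describes a functional state, and neither mentions cause. Where the protocol wants a causal condition it writes one: the primary safety endpoint in section 3.2 counts "adverse events rated as probably or definitely related to the study procedure".

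SAP 6.2 takes over the endpoint but counts dysfunction "at 3 months as adjudicated by the CEC as possibly, probably or definitely related to the study procedure". It asks for similar calculations for each event type. It then gives a reason, "Because there can be other causes (apart from surgery", and concludes that "further calculations will exclude subjects in whom the CEC determines that the event is unrelated (i.e., judged as neither possibly, probably or definitely related".

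Protocol Table 4 has five relatedness categories. The group that SAP 6.2 excludes is therefore Unrelated plus Unlikely, the latter defined as "AE has a low likelihood of being related to Aquablation procedure or AQUABEAM System".

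**The concern.** There are two conflicts. Between the documents, the SAP adds a relatedness condition that the protocol endpoint does not have, and it does not announce or justify a departure. Within SAP 6.2, the last sentence removes men whose events the first sentence has already left out of the count. The reason it gives, that dysfunction can have causes other than surgery, has force only if the first calculation included every event.

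The section also does not say whether the excluded men leave the denominator, so two analysts could follow it and report different figures.

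The endpoint is meant to support marketing claims, and the trial has no control arm. If the SAP is followed to the letter, the only rate reported depends on the CEC's attribution of cause, and it appears under the name of an endpoint that the protocol defined without attribution.

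**Working it through.** **1. The definitions side by side**

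| | Counted as an event | Denominator |
|---|---|---|
| Protocol 3.3 | Dysfunction at 3 months, any cause | Men sexually active at baseline |
| SAP 6.2, first calculation | The same, only if rated Possible, Probably or Definitely | Men sexually active at baseline |
| SAP 6.2, further calculations | The same, after excluding men whose event is Unrelated or Unlikely | Not stated |

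**2. What the further calculations do.** They exclude the exact complement of the filter already applied. Within one event type, the excluded men are not in the numerator, so it cannot change. In the composite there is one exception. A man with one related and one unrelated dysfunction could be dropped under a strict subject-level reading, and that would lower the numerator.

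**3. Is the unfiltered proportion elsewhere in the SAP?** No. Section 7 item 11 is again limited to device- or procedure-related events. Item 1 is by Clavien-Dindo class. Sections 6.6 and 6.7 and section 7 item 2 report questionnaire scores, not this proportion.

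**4. Size.** The plan states no figure for this endpoint, so there is none to reproduce. Let N be the men sexually active at baseline, x the men with a related event, and u the men whose only events are Unrelated or Unlikely. The documents give none of these. N cannot exceed the 101 treated (Protocol 2.11). All other values below are assumptions.

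- Protocol proportion: (x + u)/N.
- SAP first calculation: x/N. Gap: (x + u)/N − x/N = u/N.
- Further calculation with the denominator kept: x/N again, so the same gap.
- Further calculation with the u men dropped: x/(N − u). Gap: (x + u)/N − x/(N − u) = u(N − x − u)/(N(N − u)). This is never negative, because x + u ≤ N.

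Gaps in percentage points with x = 10:

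| N | u | u/N | Gap if the u men are dropped |
|---|---|---|---|
| any | 0 | 0 | 0 |
| 101 | 1, 2, 3 | 0.99, 1.98, 2.97 | 0.89, 1.78, 2.67 |
| 70 | 1, 2, 3 | 1.43, 2.86, 4.29 | 1.22, 2.44, 3.65 |
| 50 | 1, 2, 3 | 2.00, 4.00, 6.00 | 1.59, 3.17, 4.72 |

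**5. Examples with exact (Clopper-Pearson) 95% intervals**

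| Assumed N, x, u | Protocol 3.3 | SAP first calculation | SAP further, men dropped |
|---|---|---|---|
| 70, 10, 2 | 12/70 = 17.1% (9.2–28.0) | 10/70 = 14.3% (7.1–24.7) | 10/68 = 14.7% (7.3–25.4) |
| 75, 10, 5 | 15/75 = 20.0% (11.6–30.8) | 10/75 = 13.3% (6.6–23.2) | 10/70 = 14.3% (7.1–24.7) |

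**6. The composite exception.** With N = 75, x = 10 and u = 5, suppose one of the ten also has an unrelated dysfunction and is dropped as well. The composite becomes 9/69 = 13.0% (6.1–23.3). This is lower than 10/70, so the direction is unchanged.

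**The case against.** **Protocol 6.1 may anticipate the filter.** It says "Device- or procedure-related events which are associated with the secondary safety endpoint analysis will be as adjudicated by the CEC". Nothing in Protocol 3.3 is labelled a secondary safety endpoint, and this proportion is the natural candidate, so the SAP wording could be read as an elaboration. What stands is that the CEC's view governs whether an event counts as related. The sentence does not restrict the 3.3 endpoint to related events.

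**The conflict may be only a slip.** The last sentence of SAP 6.2 suggests that the authors meant an all-event step followed by a related-only step. This stands. A reader might infer that the SAP set out to remove the all-cause figure, and the documents do not support that: the section contradicts itself and shows no settled intent. It still has to be corrected, because its literal text omits the protocol's proportion.

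**The loss is limited.** The SAP filter keeps events rated only possibly related, so it is broader than the filter in the primary safety endpoint. Changes in MSHQ-EjD and IIEF-5 at 3 months are reported with no relatedness condition. Both points stand, and all-cause sexual function is not hidden. Mean score changes are nevertheless not the proportion of men affected.

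**The numbers are assumed.** This also stands. A reader might infer a material understatement, but u is not given and may be 0, and the intervals in the examples overlap widely. The arithmetic shows direction, not a demonstrated effect.

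**Removing the filter could count old dysfunction.** The protocol's incontinence definition requires that no pads were needed before treatment, but its ejaculatory and erectile definitions have no such condition. This stands, and the fix has to deal with it.

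**Conclusion.** SAP 6.2 is wrong as written. It does not carry the Protocol 3.3 proportion forward, and its first and last sentences cannot both be meant. Followed literally, it yields a figure equal to or lower than the protocol's under every reading of the further calculations.

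For the first calculation the shortfall is u/N. That is zero if no man has only Unrelated or Unlikely events, and 1.0 to 6.0 points for u = 1 to 3 and N = 101 down to 50. Those counts are assumptions.

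It would be too strong to say that the further calculations can never alter the numerator. That is true for each event type, but in the composite they could lower it. Nor does the point reach the primary safety conclusion, which has its own definition, or any alpha or power, because this endpoint carries no hypothesis. The change should be made because the proportion is prespecified for marketing claims and there is no comparator.

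**What to change.** Amend SAP 6.2 as follows.

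1. Delete the relatedness phrase from the first calculation. The numerator is men with ejaculatory or erectile dysfunction at 3 months, recorded as an adverse event under the protocol definitions and not already present at baseline. The denominator is men sexually active at baseline, with an exact binomial interval. The baseline condition clarifies the protocol definitions, which are silent on it, and should be stated openly as such.
2. Make the proportion with events that the CEC rates possibly, probably or definitely related the further calculation, on the same denominator. A man with only Unrelated or Unlikely events counts as having no event and is not dropped. A man with any related event counts as having one.
3. Report both proportions for the composite and for each event type.

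The cost is a few sentences and no new data collection. Protocol 2.20 already provides that "The occurrence of all adverse events will be documented in all study subjects throughout the study treatment and 12 months follow-up period", and it has the CEC rate relatedness over that period. The downside for the sponsor is that the headline rate may be somewhat higher.
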